#### 15.1.3. Primary Analysis of Primary Immunogenicity Variable(s)

The primary immunogenicity endpoints of anti-measles, anti-mumps, anti-rubella and anti-gE antibody GMCs at Day 43 will be summarized by study intervention with their 95% CI derived considering log10-transformed concentrations are normally distributed with unknown variance for antibodies against each antigen. The distribution of antibody concentration for each antigen will be graphically presented by reverse cumulative curves per study intervention. The concentration below the assay cut-off will be assigned to half the cut-off for the purpose of GMC computation. This analysis will be based on the PPS and the ES. The analysis, for PPS only, will also be repeated split by country.

Analysis Plan Page 39 of 57

Table E: Assay cut-off

Component	Assay cut-off	Method
Anti-measles Antibody	29.082 mIU/mL	
immunoglobulin (IgG)		Multiplex Luminex based Immuno Assay
Anti-mumps Antibody IgG	189.240 AU/mL	
Anti-rubella Antibody IgG	1.916 IU/mL	
Anti-gE Antibody IgG	97 mIU/mL	ELISA

Abbreviations: ELISA = Enzyme-linked immunosorbent assay

An adjusted GMC and GMC ratio with 2-sided 95% CI for study intervention which is derived from an ANOVA model on log10 transformed antibody concentration adjusted for log-transformed pre-dose antibody concentration for each antigen. The country will be added as a covariate. Study intervention will be included in the model and group contrasts with associated 2-sided 95% CI will be exponentiated to obtain study intervention GMC ratios for antibodies against each antigen and will be based on the PPS.

The GMC ratio will be estimated along with its corresponding 2-sided 95% CI by exponentiating the least-squares means for the difference.

For the interim analyses, an ANCOVA model on log-transformed anti-measles, anti-mumps, anti-rubella and antigE with MMRVNS dose level will be used as covariate in addition to the indicator of investigational vaccine.

Analysis Plan Page 40 of 57

### 15.2. Secondary Immunogenicity

#### 15.2.1. Secondary Immunogenicity Variables & Derivations

The secondary objective is to evaluate the immune response of MMRVNS vaccine (formulated with different potencies) and the MMRV vaccine (pooled group) in terms of seroresponse rates for antibodies to measles, mumps, rubella and varicella viruses at Day 43 and will be based on the PPS and ES.

## 15.2.2. Intercurrent Event Handling and Data Imputation for Secondary Immunogenicity Variable(s)

Missing data will not be replaced.

#### 15.2.3. Analysis of Secondary Immunogenicity Variables

The percentage of participants with a seroresponse will be summarized by study intervention and corresponding 2-sided 95% exact CI will be reported based on Clopper and Pearson method (Clopper CJ, 1934) for each antigen.

The analysis will also be repeated split by country. These summaries will be produced for PPS and ES.

The number and percentage of participants with a seroresponse at Day 43 for each antigen and 2-sided 95% CI on group difference in the seroresponse rate (MMRV pooled group – MMRVNS group [different potencies])- will be computed based on Miettinen and Nurminen method (Miettinen O., 1985) for PPS.

For interim analyses, seroresponse for each antibody will be analyzed using a logistic regression with MMRVNS potencies used as a covariate for PPS. The dose effect will be constrained to be positive.

Analysis Plan Page 41 of 57

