6.3.4 Blinding and Unblinding

Data will be collected in a single-blind manner. The investigator(s) and/or their staff will be aware of the study intervention assignment, but the participant will not. The study intervention will be prepared and administered by qualified study personnel who can be aware of the intervention assignment. In addition, safety evaluation by IQVIA/GSK will be conducted in a blinded manner.

Participants will be randomized in a 2:2:2:1:1 ratio to receive study intervention and will remain blinded to the study intervention throughout the course of the study.

The laboratory in charge of sample testing will be blinded to the study intervention assignment. Codes will be used to link the participant and study to each sample. There will be no link between the study intervention and the identity of the participant.

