# 3. STUDY DESIGN

# 3.1. General Description

This is a phase II, single-blind, randomized, controlled, multi-country study in healthy children of 4 to 6 years of age. Participants will be randomized to a single dose of MMRVNS vaccine (3 groups of 200 participants each receiving one of the 3 different vaccine formulations [MMRV(H)NS vaccine, MM(H)RVNS vaccine and M(L)M(L)R(L)V(L)NS vaccine respectively]) or a single dose of a comparator licensed MMVR vaccine (2 groups of 100 participants each receiving one of the 2 different lots of the MMRV vaccine [MMRV\_Lot 1 and MMRV\_Lot 2], which will be pooled for all analyses). All participants will be required to have been previously primed with a first dose of any combination of measles-, mumps-, rubella- and varicella-containing vaccine(s).

Figure A; Study Schema

Study interventions: MMRV(H)NS, MM(H)RVNS and M(L)M(L)R(L)V(L)NS = investigational vaccine in 3 different formulations; MMRV\_Lot 1 and MMRV\_Lot 2 = comparator vaccine MMRV Lot 1 and Lot 2.

Abbreviations: N = number of participants

Analysis Plan Page 22 of 57

°Before study intervention administration

\*Blood sample for anti-measles, anti-mumps, anti-rubella virus and anti-gE antibody measurements.

#Contact (by telephone call or any other convenient procedure) for the safety follow-up will take place 6 months post-dose of study intervention

Note: Visit 2 (Day 15) for review of post-vaccination safety data may be a virtual visit.

Healthy children aged 4 to 6 years will be enrolled in this study according to the inclusion and exclusion criteria (see protocol Section 5.0). Approximately 800 participants will be randomly assigned to the 5 study interventions in a 2:2:2:1:1 ratio prior to intervention to provide approximately 200 enrolled participants in each MMRVNS group and 100 enrolled participants in each MMRV group (MMRV\_Lot 1 and MMRV\_Lot 2).

Treatments will be allocated using a minimization algorithm for 90% of the participants, with the remaining 10% of treatments allocated randomly. Center and country will be used as minimization factors.

Analysis Plan Page 23 of 57

Table B: Study Groups

Study groups	Number of participants	Age (Min-max)	Study interventions
MMRV(H)NS	200	4 to 6 years	MMRV(H)NS vaccine
MM(H)RVNS	200	4 to 6 years	MM(H)RVNS vaccine
M(L)M(L)R(L)V(L)NS	200	4 to 6 years	M(L)M(L)R(L)V(L)NS vaccine
MMRV_Lot 1	100	4 to 6 years	MMRV vaccine Lot 1
MMRV_Lot 2	100	4 to 6 years	MMRV vaccine Lot 2

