# 6. GENERAL CONSIDERATIONS

Data will be summarized descriptively (frequency and percentage for categorical data and mean, standard deviation [SD] and range for continuous data, unless specified otherwise). In summary tables for categorical data for which categories are defined on the eCRF, all categories will be presented as specified, even if the participant count within that category is zero.

In all the summary tables intervention MMRV lot 1 and MMRV lot 2 will be analyzed as pooled lots.

Unless otherwise specified, all data collected during the trial will be presented in listings for the ENR.

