# 7. STATISTICAL CONSIDERATIONS

# 7.1. Adjustments for Covariates and Factors to be Included in Analyses

The following factors will be used in the analyses: country. For details, refer to section 15.1 and 15.2. The model will include all groups as fixed categorical effects in the Analysis of Variance (ANOVA) model.

For the interim analysis an Analysis of Covariance (ANCOVA) model on log-transformed anti-measles, anti-mumps, anti-rubella and anti-gE with MMRVNS dose level will be used as covariate in addition to the indicator of investigational vaccine. Likewise, seroresponse will be analyzed using a logistic regression with the same covariate. The dose effect will be constrained to be positive.

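### The seroresponse difference is not stratified by country, although allocation is minimised on country, SAP 7.1 names it as an analysis factor and the GMC ratio is adjusted for it

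*SAP*

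**What the plan says.** - **Allocation.** SAP 3.1: "Treatments will be allocated using a minimization algorithm for 90% of the participants, with the remaining 10% of treatments allocated randomly", and "Center and country will be used as minimization factors". Protocol 6.3.2 and 6.3.3 name the same two factors. The ratio is 2:2:2:1:1 (Protocol 6.3.4). Because SAP 6 states that "intervention MMRV lot 1 and MMRV lot 2 will be analyzed as pooled lots", the four analysed groups are of equal planned size.
- **Factors in the analysis.** SAP 7.1: "The following factors will be used in the analyses: country". It then refers the reader to sections 15.1 and 15.2 for details.
- **GMC ratio.** SAP 15.1.3 adjusts for pre-dose concentration, and "The country will be added as a covariate". Protocol 9.3.2.2 agrees.
- **Seroresponse difference.** SAP 15.2.3: the interval on the group difference "will be computed based on Miettinen and Nurminen method", on the Per Protocol Set. Neither this section nor Protocol 9.3.3.1 states strata or covariates. Country enters 15.2.3 only through the within-group rates: "The analysis will also be repeated split by country".

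**The concern.** There are two linked problems.

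The first needs no numerical assumption. SAP 7.1 sends the reader to 15.2 for the use of country, but 15.2.3 does not use country in the between-group comparison. A programmer working from 7.1 could stratify; one working from 15.2.3 would not.

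The second is statistical. Balancing groups on a factor removes that factor's contribution to the variability of the group difference. An interval that ignores the factor still counts that contribution, so it is conservative to the extent that the factor is related to the outcome. In a descriptive trial the estimates and intervals are the main comparative output, so the two immunogenicity endpoints should be handled alike unless there is a stated reason.

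**Working it through.** **1. The plan's own precision figure.** Protocol 9.5 gives a 1.25-fold half-width for the GMC ratio, with 160 evaluable per group (pooled comparator 2 × 80) and 0.45 on the log10 scale, read as a standard deviation:

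10^(1.96 × 0.45 × √(2/160)) = 10^0.0986 = 1.255.

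The figure reproduces with no country, centre or baseline term. It concerns the GMC ratio only; the documents give no precision statement for seroresponse.

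**2. Seroresponse difference under assumed country rates.** Inputs: n = 160 per group from Protocol 9.5. Two equal countries, the same rates in both groups and the rates themselves are my assumptions. With p the average rate and p_k the country rates, the large-sample half-widths are:

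- unstratified: 1.96 × √(2 × p(1−p)/160)
- stratified by country: 1.96 × √(2 × mean of p_k(1−p_k)/160)

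For 98% and 90%: p = 0.94 and p(1−p) = 0.0564. The stratum mean is (0.0196 + 0.0900)/2 = 0.0548. The half-widths are 1.96 × √0.000705 = 5.20 points and 1.96 × √0.000685 = 5.13 points.

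| Assumed country rates | p(1−p) | Mean p_k(1−p_k) | Unstratified (points) | Stratified (points) | Change in width |
|---|---|---|---|---|---|
| equal | same | same | same | same | 0 |
| 99% / 97% | 0.0196 | 0.0195 | 3.07 | 3.06 | −0.3% |
| 98% / 90% | 0.0564 | 0.0548 | 5.20 | 5.13 | −1.4% |
| 98% / 80% | 0.0979 | 0.0898 | 6.86 | 6.57 | −4.2% |
| 90% / 60% | 0.1875 | 0.1650 | 9.49 | 8.90 | −6.2% |

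The last column is √(stratified term/unstratified term) − 1. These formulas show the relative gain. Near 100% an actual Miettinen-Nurminen interval is wider than they suggest: 3.71 to 3.74 points at a 98% rate in the simulation below.

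**3. Cost of stratifying when country matters little.** This was simulated with actual Miettinen-Nurminen intervals, 90% minimised and 10% random allocation, and 20% loss. Assumptions: 5 countries, 20 or 60 centres, rates of 85% or 98%, no treatment difference, 250 runs per scenario. Outcome variation was placed between centres (intraclass correlation 0 to 0.10) with no separate country effect, so little gain from stratifying by country was to be expected. Across the 12 scenarios the mean half-width changed by between −0.006 points (7.855 to 7.849) and +0.031 points (3.736 to 3.767). Stratifying by country costs almost nothing when it is not needed.

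**The case against.** The strongest reply is that nothing in the documents shows rates differing by country.

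- Protocol 4.2 and 4.4 restrict countries to those whose schedule is aligned with the US.
- Protocol 5.1 requires priming in the second year of life, and 5.2 excludes a history of the four diseases or a previous second dose.
- SAP 3.3 expects few initially seronegative children, so a country rate as low as 60% after a second dose is hard to motivate.
- The SAP follows the method in Protocol 9.3.3.1, shows rates by country, and no hypothesis or margin depends on the interval. The pointer in 7.1 to 15.2 could refer to those by-country tables.

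Most of this stands, and it makes the lower rows of the table unlikely. It does not explain why country is in the GMC comparison and absent from the seroresponse comparison. By-country tables of within-group rates also do not give a country-adjusted difference.

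A reader might go further and infer that the intervals for both endpoints are wider than the design supports, or that centre must also enter the analysis. The documents do not support either inference. They give no between-country or between-centre variance, and the only precision target, 1.25-fold, is reproduced without any adjustment. The GMC model already contains country and pre-dose level. If 5% or 10% of the variance lay between centres, both assumed values, removing it would move the 1.255-fold half-width only to 1.248 or 1.240. With fixed centre effects and no true centre variation, 60 centres widened it from 1.256 to 1.261. A random centre intercept avoided that penalty in simulation, but it needs a rule for small centres and its benefit depends on an unknown variance. Stratifying the seroresponse interval by centre widened it in every scenario, by 0.03 points (7.855 to 7.880) up to 0.84 points (3.712 to 4.548).

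**Conclusion.** The point holds as a minor inconsistency with an inexpensive remedy. SAP 7.1 and 15.2.3 do not agree on the use of country, and the seroresponse difference leaves out a factor on which allocation is balanced and for which the other immunogenicity comparison is adjusted.

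Any resulting error is in the conservative direction. On the assumptions of 160 per group and two equal countries, it ranges from essentially nothing when rates are similar, through 0.07 points of half-width at 98%/90%, to 0.29 points at 98%/80% (6.86 − 6.57). That the intervals are in fact too wide is not established. Leaving centre out of the GMC model is a defensible choice on the information given.

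**What to change.** - In SAP 15.2.3, compute the seroresponse difference and its 95% CI by the Miettinen-Nurminen method stratified by country on the Per Protocol Set. State the stratum weights, for example n1·n2/(n1+n2) as used in the simulation, and how a country with no participants in one group is handled.
- Keep the unstratified interval as supportive.
- Reword SAP 7.1 so that its reference to 15.2 matches, and record the stratification in SAP 3.3, because Protocol 9.3.3.1 states no strata.

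The cost is SAP wording and a program option, with no new data. The weighted difference may not exactly equal the difference of the tabulated rates, so the table needs a footnote. No change to the GMC model is proposed.

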#### 16. SAFETY OUTCOMES

All outputs for safety outcomes will be based on the ES.

There will be no statistical comparisons between the study interventions for safety data.

Secondary Safety Endpoints:

#### Solicited events

- Percentage of participants reporting each solicited administration site event during the 4-day
   period (day of administration and 3 following days) after the dose of study intervention
- Percentage of participants reporting each solicited systemic event in terms of drowsiness and loss of appetite during the 4-day period (day of administration and 3 following days) after the dose of study intervention
- Percentage of participants reporting each solicited systemic event in terms of fever, measles/rubella-like rash, varicella-like rash and other rash (not measles/rubella-like rash or varicella-like rash) during the 43-day period (day of administration and 42 following days) after the dose of study intervention

#### Unsolicited adverse events

- Percentage of participants reporting unsolicited AEs during the 43-day period (day of administration and 42 following days) after the dose of study intervention
- Serious adverse events

Analysis Plan Page 42 of 57

 Percentage of participants reporting SAEs after the dose of study intervention up to the end of study

#### 16.1. Adverse Events

Adverse Events will be coded using MedDRA central coding dictionary, Version 27.0 or higher. Adverse events will be described using frequency and percentage.

Adverse Events will be grouped by SOC and PT and summarized by study intervention at time of onset of the AE.

The summary tables will present the number and percentage of total participants and number of events, by SOC and by PT for each study intervention.

For the summaries of AEs, participants who experience the same AE (in terms of the MedDRA SOC and PT) more than once will only be counted once for that event in the number of participants but all occurrences of the same event will be counted in the number of events.

See APPENDIX 2 for handling of partial dates for AEs. In the case where it is not possible to define an AE as pretreatment or treatment-emergent (TEAE) due to missing or partial dates, the AE will be classified by the worst case; i.e., TEAE. TEAE are defined as AEs which commence on or after the time of the study intervention through to the study end. All AE summaries will be restricted to TEAEs only.

Listings of all AEs and SAEs leading to discontinuation from the study will be provided.

Analysis Plan Page 43 of 57

#### 16.1.1. Solicited Adverse Events

Solicited events are recorded in electronic diaries. Duplicate entries are defined as records with identical participant ID, category, object of the observation, date and time of collection, result or finding in original units and evaluator. In case of duplicate records, the first record will be kept for analysis. The first record is determined by sequence number assigned in the SDTM dataset. In the case of duplicate entries with differing result, the worst case record will be kept for analysis.

In the event the electronic diary was started later than the day of vaccination, it remained open to record solicited events beyond the end of the solicited periods. Data beyond the solicited period will remain in the datasets but will not be used in the statistical analysis, since the solicited period is based on Study Day for the statistical analyses, see section 6.1.

For each study intervention and each solicited event, the incidence rates (frequencies and percentages) of vaccinated participants with solicited administration site events collected within 4 days (Day 1 to Day 4), systemic events (drowsiness and loss of appetite) collected within 4 days (Day 1 to Day 4) and systemic events (fever, measles/rubella-like rash, varicella-like rash and other rash [not measles/rubella-like rash or varicella-like rash]) collected within 43 days (Day 1 to Day 43) will be summarized (percentage of vaccinated participants with each of any, grade 2 or 3, related, grade 3 leading to medical attention). The completeness defined as the percentage of vaccinated participants who documented presence/absence of each event as well as the daily prevalence of each symptom among vaccinated participants who documented presence /absence of the event on that day will be provided. These will also be summarized for each country.

The duration of each solicited event, in days, will be summarized using descriptive statistics (n, mean, standard

Analysis Plan Page 44 of 57

deviation, median and range) for each study intervention. The duration will be calculated from the first date that the symptom was reported up to the last date the symptom was reported ignoring any dates when the symptom was absent or was not recorded:

Last date symptom recorded - first date symptom recorded + 1

The number of solicited events still ongoing at the end of the solicited period will be summarized by study intervention by maximum intensity (any, grade 2-3 and grade 3).

**Table F:** Solicited events

Solicited administration site events	Solicited systemic events
Pain at Injection Site	Drowsiness
Redness at Injection Site	Loss of appetite
Swelling at Injection Site	Fever
	Measles/rubella-like rash
	Varicella-like rash
	Other rash (not measles/rubella-like rash or varicella-like rash)

Table G: Intensity Scales for Solicited Events in Children (4 to 6 years of Age)

Adverse Event	MedDRA Lower Level Term	Intensity Grade	Parameter
	Administration site pain (10058049)	0	None
		1	Mild: Minor reaction to touch
Pain at Injection Site		2	Moderate: Cries/protests on touch
		3	Severe: Cries when limb is moved/spontaneously painful

Analysis Plan Page 45 of 57

Adverse Event	MedDRA Lower Level Term	Intensity Grade	Parameter
Administration site erythema	0	None	
Redness at Injection	(10074796)	1	> 0 - ≤ 5 mm
Site		2	> 5 - ≤ 20 mm
		3	> 20 mm
	Administration	0	None
Swelling at Injection	site swelling (10075107)	1	> 0 - ≤ 5 mm
Site		2	> 5 - ≤ 20 mm
		3	> 20 mm
	Pyrexia	0	<38.0°C (100.4°F)
E*	(10037660)	1	≥ 38.0°C (≥ 100.4°F) - ≤ 39.0°C (≥ 102.2°F)
Fever*		2	> 39.0°C (≥ 102.2°F) - ≤ 39.5°C (≥ 103.1°F)
		3	> 39.5°C (≥ 103.1°F)
	Maculopapular	0	None
Measles/rubella-like rash (10037898)	1	1-25 lesions	
rash	(10057050)	2	26-50 lesions
		3	≥51 lesions
	Rash vesicular	0	None
Varicella-like rash	(10052566)	1	1-25 lesions
v at icelia-like t asii		2	26-50 lesions
		3	≥51 lesions
		0	None
Other rash (not measles/rubella-like rash or varicella- like)	(10049201)	1	Mild: Rash which is easily tolerated by the child, causing minimal discomfort and not interfering with everyday activities
		2	Moderate: Rash which is sufficiently discomforting to interfere with normal everyday activities
		3	Severe: Rash care and would cause the parent(s)/LAR(s) to seek medical advice

Analysis Plan Page 46 of 57

Adverse Event	MedDRA Lower Level Term	Intensity Grade	Parameter
	Drowsiness	0	Behaviour as usual
	(10013649)	1	Mild: Drowsiness easily tolerated
Drowsiness		2	Moderate: Drowsiness that interferes with normal activity
		3	Severe: Drowsiness that prevents normal activity which prevents normal, everyday activities (in a young child, such an AE would, for example, prevent attendance at school/day
	Decreased	0	Appetite as usual
Loss of appetite (10061428)	1	1	Mild: Eating less than usual/ no effect on normal activity
		2	Moderate: Eating less than usual/ interferes with normal activity
		3	Severe: Not eating at all

\* Temperature will be analyzed in 0.5°C increments from ≥ 38.0°C (≥ 100.4°F)

The number and percentage of participants per study intervention reporting unsolicited adverse events with MedDRA preferred terms that are synonymous with solicited adverse events, and starting after the end of each solicited period, will be summarized by severity (mild, moderate or severe). If a participant experiences an event on more than one occasion, the maximum intensity will be reported. The following table shows the corresponding MedDRA preferred terms or higher level terms that will be selected from the unsolicited adverse events for this analysis.

Table H: Unsolicted adverse events that are synonymous with soicted adverse events

Solicited Adverse Event	MedDRA PT/HLT

Analysis Plan Page 47 of 57

Pain at injection site	Administration site pain (PT)
Redness at injection site	Administration site erythema (PT)
Swelling at injection site	Administration site swelling (PT)
Drowsiness	Somnolence (PT)
Loss of appetite	Decreased appetite (PT)
Fever	Pyrexia (PT)
Rash (all types combined)	Rashes, eruptions and exanthems NEC (HLT)

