8.3 Adverse Events, Serious Adverse Events, and Other Safety Reporting

8.3.1 Time Period and Frequency for Collecting AE and SAEs and Other Safety Information

The definitions of an AE or SAE are provided in Appendix 3.

Collection of AEs starts on the day of the study intervention (Day 1) up to Day 43 unless the AE leads to study discontinuation. Collection of SAEs starts the day of the study intervention (Day 1) and up to study end (Day 181) unless the SAE leads to study discontinuation. The frequency for collection of AEs and SAEs is shown in the SoA (Section 1.3).

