Secondary	Randomized MMRVNS vaccine or MMRV vaccine	Healthy children of 4 to 6 years of age	Each solicited administration site event within 4 days after dose of study intervention	eDiary not completed     on each day	Missing data won't be imputed. Compliance to eDiary will be captured	Percentage of participants with event will be summarized with exact 95% Confidence Interval (CI)
Secondary	Randomized MMRVNS vaccine or MMRV vaccine	Healthy children of 4 to 6 years of age	Each solicited systemic event (drowsiness and loss of appetite) within 4 days after dose of	eDiary not completed     on each day	Missing data won't be imputed. Compliance to eDiary will be captured	Percentage of participants with event will be summarized with exact 95% Confidence Interval (CI)

Analysis Plan Page 20 of 57

			study intervention			
Secondary	Randomized MMRVNS vaccine or MMRV vaccine	Healthy children of 4 to 6 years of age	Each solicited systemic event (fever, measles/rubella-like rash, varicella-like rash and other rash) within 43 days after dose of study intervention	eDiary not completed     on each day	Missing data won't be imputed. Compliance to eDiary will be captured	Percentage of participants with event will be summarized with exact 95% Confidence Interval (CI)
Secondary	Randomized MMRVNS vaccine or MMRV vaccine	Healthy children of 4 to 6 years of age	Each unsolicited adverse event within 43 days after dose of study intervention	Permanently     discontinued from study     due to any reasons prior     to Day 43 blood     sampling	Missing data won't be imputed. Summaries will present the actual data.	Percentage of participants with event will be summarized with exact 95% CI
Secondary	Randomized MMRVNS vaccine or MMRV vaccine	Healthy children of 4 to 6 years of age	Serious Adverse Events from dose of study intervention up to study end	Permanently     discontinued from study     due to any reasons	Missing data won't be imputed. Summaries will present the actual data.	Percentage of participants with event will be summarized with exact 95% CI

[figure not shown]
Analysis Plan Page 21 of 57

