#### 16.1.1.1. eCOA Compliance

Overall electronic diary (eCOA) compliance (across all eCOAs and all participants) for the study is calculated as:

Where the expected number of complete eCOAs per participant is defined as 43, the number of days in which the eCOA is expected to be completed. This definition will also apply to participants who discontinue the study early.

An eCOA is considered complete if there is no missing data within the assessment. Solicited event data reported by the investigator will not contribute to eCOA compliance. On days when the option to select "no symptoms to report" is available and there are no occurrences of the symptoms solicited for on that day, an eCOA will be considered

Analysis Plan Page 48 of 57

complete if the temperature result is available.

A participant is considered to be compliant with their eCOA if at least 80% of their eCOA are complete, i.e, a participant is compliant if they meet the following criteria:

$$\frac{Total\ number\ of\ complete\ eCOAs}{Expected\ number\ of\ complete\ eCOAs}$$
 × 100 ≥ 80%

The overall compliance, and the number of participants who are 0 - <50% compliant, 50 - <80% compliant and ≥80% compliant with eCOA assessments will be summarized.

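### Solicited-event incidence is divided by all vaccinated children, so a child with no diary record counts in effect as event-free, and completeness is defined without a day rule

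*SAP*

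**What the plan says.** SAP 16 states that "All outputs for safety outcomes will be based on the ES", and SAP 5.3 defines that set as everyone dosed. SAP 16.1.1 gives the incidence of each solicited event as "percentage of vaccinated participants with each of any, grade 2 or 3, related, grade 3 leading to medical attention". The next sentence adds two outputs. One is "The completeness defined as the percentage of vaccinated participants who documented presence/absence of each event". The other is "daily prevalence of each symptom among vaccinated participants who documented presence /absence of the event on that day". SAP Table A says that missing diary data are not imputed and that "Compliance to eDiary will be captured", with an exact 95% CI for the percentage with the event.

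On late diaries, SAP 16.1.1 says: "In the event the electronic diary was started later than the day of vaccination, it remained open". Entries after the solicited period are kept in the datasets but not analysed. SAP 16.1.1.1 measures compliance against 43 expected diary days and calls a child compliant at 80% or more. It adds that "Solicited event data reported by the investigator will not contribute to eCOA compliance", so such reports are foreseen.

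On timing, Protocol 8.3.1 says: "Collection of AEs starts on the day of the study intervention (Day 1) up to Day 43". Protocol 10.3.10 sets the same period for fever, rashes and unsolicited events. The Schedule of Activities (Protocol 1.3) puts diary return and the last non-serious AE recording at Visit 3. Table 4 allows Visit 3 from 35 to 56 days after Visit 1.

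**The concern.** One sentence of SAP 16.1.1 uses all vaccinated children as the denominator and the next uses only those who documented the day. For incidence, a child whose parent recorded nothing for an event stays in the denominator and cannot reach the numerator unless the investigator reports the event. The SAP does not say outright that such a child is event-free. That follows from the denominator together with the no-imputation rule.

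These percentages are secondary safety endpoints, and the error runs toward better apparent tolerability. The exact CI is affected too, because undocumented children count as observed. Completeness could let a reader rescale, but only if it is known whether one documented day or every day is required.

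The timing issue is separate. If Visit 3 is early, the diary goes back and scheduled non-serious AE recording ends before Day 43. Protocol 10.3.4 collects events that were neither medically attended nor of concern to the parent at the next visit. After Visit 3 only the Day 181 contact remains, and the Schedule marks that contact for SAEs and not for non-serious AEs.

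**Working it through.** The plan gives no expected incidence and no diary completion rate, so it has no figure of its own to reproduce here. The documented shares below are assumptions.

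**Inputs.** 200 children per group (Protocol 4.1, with the comparator lots pooled); 4-day and 43-day periods (SAP 16.1.1); 43 expected diary days and the 80% threshold (SAP 16.1.1.1); Visit 3 interval of 35 to 56 days (Protocol Table 4); Study Day = date difference + 1 (SAP 6.1).

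**1. Effect on incidence.** Let c be the share of children with at least one in-window record. Assume documentation is unrelated to having the event, and that no events are reported for the rest. Then reported rate = true rate × c. With a true 30.0% and Clopper-Pearson intervals:

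| Documented (assumed) | Among documented | Among all vaccinated |
|---|---|---|
| 95% | 57/190 = 30.0% (23.6 to 37.1) | 57/200 = 28.5% (22.4 to 35.3) |
| 90% | 54/180 = 30.0% (23.4 to 37.3) | 54/200 = 27.0% (21.0 to 33.7) |

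The relative understatement equals the undocumented share.

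**2. Rare events.** With zero events the upper limit is 1 − 0.025^(1/n): 1.83% for n = 200, against 1.92% for n = 190 and 2.03% for n = 180.

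**3. Why completeness needs a day rule.** Suppose, as an assumption, that each day is documented independently with probability 98% or 95%.
- Every day required, 4-day period: 0.98^4 = 92.2%; 0.95^4 = 81.5%.
- Every day required, 43-day period: 0.98^43 = 41.9%; 0.95^43 = 11.0%.
- Any one day required: 1 − 0.05^4 = 99.9994% in the least favourable of the four cases.

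Dividing the reported rate by completeness recovers the rate among the documented only under the any-day reading. Even then it does not correct the interval.

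**4. Whether the compliance bands fill the gap.** The threshold is 0.80 × 43 = 34.4, so 35 complete days suffice. A child with nothing on Days 1 to 4 and everything afterwards scores 39/43 = 90.7% and counts as compliant, with no record for any 4-day endpoint.

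**5. Early Visit 3.** The earliest allowed visit is Study Day 35 + 1 = 36, which leaves Days 37 to 43, or 7/43 = 16.3% of the period for that child. If visits were uniform over the 22 allowed intervals, 7 would fall short of 42 days with a mean loss of 4 days. With uniform onsets the group loss is 7/22 × 4/43 = 3.0%. If 10% of children came early, it is 0.10 × 4/43 = 0.9%. These patterns are assumptions, and Table 4 asks sites to keep to the planned 42 days where possible.

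**The case against.** The endpoint is the percentage of participants reporting each event, so an all-vaccinated percentage is that endpoint as written and agrees with Protocol 9.3.3.2. This stands, and it is why that figure should be kept.

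The safeguards are real. The Schedule of Activities has diary training at Visit 1, a reminder at the Day 2-3 call, and diary review at that call, Visit 2 and Visit 3. The call is allowed 1 to 3 days after Visit 1, which is Study Days 2 to 4, so a diary not yet started can be caught inside the 4-day window. Compliance bands, completeness and daily prevalence are all planned outputs. The table templates that accompany the SAP are not among the documents reviewed and may hold a day rule.

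Under the independent-day model above, almost every child has at least one record, so the added denominator would change very little. It helps only where whole windows are missing, for example when a diary is opened after Day 4. Scattered missing days remain unaddressed. This also stands.

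Three stronger readings are tempting, and the documents support none of them.
- That completeness is undefined: SAP 16.1.1 defines it and omits only the number of days.
- That a large share of children is undocumented: no passage gives a share, and the 20% in Protocol 9.5 concerns evaluability for the primary objective.
- That the comparison between vaccines is biased: nothing points to documentation differing by arm, parents are blinded (Protocol Appendix 4), and SAP 16 plans no statistical comparison of safety between arms.

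On timing, medically attended or worrying events are to be reported to the site as soon as possible, so only scheduled collection ends early. SAP version 5.0 is dated December 2024 and speaks of diaries in the past tense, so a schedule change may come too late.

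**Conclusion.** The point holds as a modest reporting gap. Where a child has no in-window record for an event, the planned percentage in effect counts that child as event-free. It then understates incidence by the undocumented share and makes the exact upper limit too low. That share cannot be known from the documents. The loss is 1.5 percentage points at a true 30% if 5% are undocumented and 3.0 points if 10% are, under the assumptions stated, and it is nil with full documentation. Completeness lacks a day rule, and the 43-day compliance bands cannot stand in for one. There are no hypotheses (Protocol 9.1), so the consequence is confined to descriptive rates and their intervals.

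The mismatch between Study Day 36 and Day 43 is genuine but minor. It touches fever, rashes and non-serious unsolicited AEs. It does not touch SAEs or the 4-day solicited events.

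**What to change.** **SAP 16.1.1.**
- Keep the all-vaccinated percentage.
- Add, for each event, incidence with an exact 95% CI among Exposed Set participants with at least one documented in-window record for that event, counting investigator-reported events as records.
- Define completeness on the same at-least-one-record basis, and show it separately for the 4-day and 43-day periods and by group.
- State whether choosing the no-symptoms option counts as documented absence. SAP 16.1.1.1 settles this for compliance only.
- Label the added figure as addressing missing participants, not missing days.

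The cost is a few sentences and one extra column or table. The denominator is smaller and the interval wider. The figure may overstate incidence if parents, or investigators reporting for them, document more often when symptoms occur.

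**Timing.** The Schedule of Activities, Table 4 and the Day 1 to 43 recording period must be reconciled. If collection is over, report by group the number of children with Visit 3 before Day 43 and the days observed. The cost is a clarification to sites or one descriptive table.
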